6.3 DLT Analysis Set

The analysis of DLT will be conducted on the DLT Analysis Set defined as all subjects that are enrolled and receive at least 1 dose of AMG 160 with an evaluable DLT endpoint.

The DLT endpoint is evaluable if either:

- 1) the subject experiences a DLT; or
- 2) the subject does not experience a DLT after receiving all planned doses within the 28-day DLT window in cycle 1.

7. Planned Analyses

7.1 Interim Analysis and Early Stopping Guidelines

Safety data will be reviewed on an ongoing basis.

During dose exploration and formally during dose level review meetings (DLRMs), Amgen, in consultation with the site investigators, will review all available cumulative data by cohort prior to making dose escalation or dose de-escalation recommendations.

Adverse events and DLTs observed in all subjects will be evaluated continually and fully integrated into all DLRMs and considered in all enrollment and dosing decisions. During dose expansion, Amgen will conduct evaluations of the ongoing grade 4 or higher treatment-related adverse event rate to assess if the threshold for possible early trial termination has been reached. If this threshold is met, enrollment to dose expansion will be halted pending review of safety data by the DLRT. After receiving the DLRT recommendation, Amgen will choose to take one of the following actions.

- 1) Terminate the trial
- 2) Amend the protocol to potentially improve the benefit/risk for subjects (eg, increase safety monitoring, modify dose/schedule, mandate [REDACTED])
- 3) Continue dose expansion without any changes

The stopping rules use a Bayesian approach proposed by Thall et al, 1995 to terminate the study if the posterior probability that the grade 4 or higher treatment-related adverse event rate is greater than 20% is $> 80\%$. The stopping boundaries assume a prior distribution of Beta (0.40, 1.60) are presented in [Table 7-1](#) and the operating characteristics with pre-specified batch size of 10 new subjects per batch are presented in [Table 7-2](#). The operating characteristics in [Table 7-2](#) provide the probability of stopping the trial early for given hypothetical true rate of grade 4 or higher treatment-related adverse events, whereas the stopping criteria in [Table 7-2](#) are based on situations where the empirical evidence would result in a posterior probability of $\geq 80\%$ that the true grade 4 or higher treatment-related adverse event rate is $\geq 20\%$.

Table 7-1. Stopping Boundary for Dose Expansion With Posterior Probability of 80% and Grade 4 or Higher Treatment-related Adverse Event Limit of 20%

Number of Subjects	Stop Study if Observing These Many Grade 4 or Higher Treatment-related Adverse Events
10	≥ 4
20	≥ 6
30	≥ 9
40	Dose Expansion Complete

Table 7-2. Operating Characteristics With Batch Size of 10 Subjects

True Grade 4 or Higher Treatment-related Adverse Event Rate	Probability of Early Stopping of Dose Expansion	Average Dose Expansion Sample Size
0.10	2.0%	39.5
0.15	9.1%	37.6

0.20	23.2%	33.9
0.25	42.2%	28.8
0.30	61.6%	23.4

A formal interim analysis of available safety and efficacy data will occur when the first 10 evaluable subjects enrolled have had the opportunity to complete 4 months on study. This interim analysis will estimate MTD, support the determination of RP2D, conduct futility analysis of objective response rate (ORR), and support the evaluation of benefit/risk profile of AMG 160 as a monotherapy.

When deemed necessary, the scope of this interim analysis may include other endpoints mentioned in [Section 2.1](#) if applicable. However, analysis of DOR and time-to-event endpoints will not be conducted unless there are more than 10 events.

[figure not shown]
A futility analysis of ORR will be performed using Bayesian predictive probability (Lee and Liu, 2008) when the first 10 evaluable subjects reach month 4. If the predictive probability of observing ORR response > 15% at the end of the study with 50 evaluable subjects is less than 30%, the study may stop early (pT = 0.25). Equivalently, if we observe ≥ 1 objective responder in the first 10 subjects, an additional subjects (up to 40) will be enrolled into the expansion cohort. The predictive probability is calculated with a noninformative prior, Jeffreys prior, Beta(0.5, 0.5).

Similarly, futility analysis will also be conducted during the expansion cohort. The stopping boundaries are presented in [Table 7-3](#). The operating characteristics in [Figure 7-1](#) provide the probability of stopping the trial early for given hypothetical true rate of ORR.

Table 7-3. Objective Response Rate Stopping Boundary

Number of Evaluable Subjects Each Month 4	Stop Study if Observed Objective Response Rate (ORR) Response
10	< 1
20	< 2
30	< 3
40	< 4
50	Study Complete

Figure 7-1. The Probability of Stopping The Trial Early

Data will be subject to ongoing checks for integrity, completeness and accuracy in accordance with the Data Management Plan, however there is no requirement to resolve outstanding data issues ahead of the snapshot. The data will be taken “as-is” on the day of snapshot for futility analysis. No locking is performed and the “as-is” snapshot of the database will be used in the futility analysis. Data will be subject to ongoing checks for integrity, completeness and accuracy in accordance with the Data Management Plan with the expectation that all outstanding data issues are resolved ahead of the snapshot for the formal interim analysis. The data will be locked to prevent further changes, and a snapshot of the locked database will be used in the formal interim analysis.

7.1.1 Stopping Rules for Treatment With Siltuximab

Amgen will conduct evaluations of the treatment and outcome of the CRS events treated with siltuximab on an ongoing basis to assess if the threshold for pausing siltuximab treatment has been reached as outlined in the table below. If these stopping rules are met, an ad hoc DLRM will be triggered to review safety data and available PK, [REDACTED], and efficacy data. If recommended by DLRT, the use of siltuximab will resume. The stopping rules to trigger an adhoc DLRM to

review siltuximab treatment use a Bayesian approach proposed by Thall et al, 1995; an adhoc DLRM will be triggered if the posterior probability that the CRS progression to grade 3 rate is greater than 30% is $> 80\%$ or the posterior probability that the CRS progression to grade 4 rate is greater than 10% is $> 80\%$; or observation of any grade 5 CRS after the event has been treated with siltuximab. The stopping boundaries presented below assume a prior distribution of Beta (0.6, 1.4) for progression to grade 3 CRS and a prior distribution frequently if necessary to address emerging safety concerns. If the triggered adhoc DLRM coincides with the regular DLRM, they may be combined.

Number of subjects treated with siltuximab	Trigger DLRM if severity of any CRS event treated with siltuximab progresses to Grade 5	
	Or this number of subjects with severity of CRS progressed to Grade 3 after being treated with siltuximab	Or this number of subjects with severity of CRS progressed to Grade 4 after being treated with siltuximab
5	≥ 3	≥ 2
10	≥ 5	≥ 3
15	≥ 7	≥ 3
20	≥ 8	≥ 4
25	≥ 10	≥ 5
30	≥ 12	≥ 5
35	≥ 13	≥ 6
40	≥ 15	≥ 6

7.2 Primary Analysis

The primary analysis for the dose-exploration phase will occur when target enrollment is complete and each subject either completes 6 months on the study or withdraws from the study.

The primary analysis for time to event endpoints (eg, duration of response, PFS, and 1-year overall survival [OS]) will occur when target enrollment is complete for the dose expansion phase and each subject either completes 1 year on study or withdraws from the study.

Data will be subject to ongoing checks for integrity, completeness and accuracy in accordance with the Data Management Plan with the expectation that all outstanding data issues are resolved ahead of the snapshot. The data will be locked to prevent further changes, and a snapshot of the locked database will be used in the analysis.

7.3 Final Analysis

The final analysis will occur when target enrollment is complete for both phases and all subjects have ended the study.

Data will be subject to ongoing checks for integrity, completeness and accuracy in accordance with the Data Management Plan with the expectation that all outstanding data issues are resolved ahead of the snapshot. The data will be locked to prevent further changes, and a snapshot of the locked database will be used in the analysis.

8. Data Screening and Acceptance

8.1 General Principles

The objective of the data screening is to assess the quantity, quality, and statistical characteristics of the data relative to the requirements of the planned analyses.

8.2 Data Handling and Electronic Transfer of Data

The Amgen Global Study Operations-Data Management (GSO-DM) department will provide all data to be used in the planned analyses. This study will use the RAVE database.

8.3 Handling of Missing and Incomplete Data

Subjects may miss specific data points for a variety of causes. In general, data could be missing due to a subject's early withdrawal from the study, a missed visit, or inability to evaluate an endpoint at a particular point in time.

In general, the safety analysis set will be used without any imputation for missing data for the primary and secondary endpoints. [REDACTED]

8.4 Detection of Bias

Lack of protocol compliance and the potential for biased statistical analyses will be examined by assessing the incidence of important protocol deviations. The clinical study team will identify and document the criteria for important protocol deviations.

8.5 Outliers

Pharmacokinetics (PK) concentration data will be evaluated for outliers by visual inspection, and decision to re-assay individual samples will be made in accordance with standard pharmacokinetic evaluation practice.

Descriptive statistics will be used to identify potential outliers in key variables. Suspected outliers will be included in the analyses unless there is sufficient scientific justification to exclude them.

8.6 Distributional Characteristics

Where appropriate, the assumptions underlying the proposed statistical methodologies will be assessed. If required data transformations or alternative non-parametric methods of analyses will be utilized.

8.7 Validation of Statistical Analyses

Programs will be developed, maintained, and output will be verified in accordance with current risk-based quality control procedures.

Tables, figures, and listings will be produced with validated standard macro programs where standard macros can produce the specified outputs.

The production environment for statistical analyses consists of Amgen-supported versions of statistical analysis software; for example, the SAS System version 9.4 or later.

9. Statistical Methods of Analysis

9.1 General Considerations

Descriptive statistics will be provided for selected demographics, safety, PK, efficacy, [REDACTED] by dose, dose schedule, and time as appropriate. Descriptive

statistics on continuous data will include means, medians, standard deviations and ranges, while categorical data will be summarized using frequency counts and percentages. Graphical summaries of the data may also be presented.

Confidence intervals (CI) for proportions will be estimated using an exact method proposed by Clopper-Pearson ([Clopper and Pearson, 1934](#)). Kaplan-Meier methods will be used to estimate the median and percentiles for time to event endpoints with CI calculated using the Brookmeyer and Crowley ([Brookmeyer and Crowley, 1982](#)) method. Kaplan-Meier methods will be used to estimate landmarks for time to event endpoints (eg, 1-year overall survival [OS]) with the Greenwood formula ([Kalbfleisch and Prentice, 1980](#)) used to estimate the standard error used in CI calculation.

Greenwood formula will be used for landmark analysis, and for other time-to event analysis the Brookmeyer and Crowley formula will be used. We will be only doing the landmark analysis for OS.

9.2 Subject Accountability

The number and percent of subjects who were enrolled and received the investigational product, discontinued from AMG 160 (including reasons for discontinuing), completed study, discontinued the study (including reasons for discontinuing) will be summarized.

Key study dates for the first subject enrolled, the last subject enrolled, and last subject's end of study will be presented.

A subject listing and summary noting inclusion in each analysis subset will be provided for all subjects enrolled. A subject listing noting AMG 160 administration start and end time, reason for discontinuation of treatment, and reason for discontinuing the study will be provided. A list of subjects screened but not enrolled (screen failures) may be provided.

9.3 Important Protocol Deviations

Important Protocol Deviations (IPDs) categories are defined by the study team before the first subject's initial visit and updated during the IPD reviews throughout the study prior to database lock. These definitions of IPD categories, subcategory codes, and descriptions will be used during the course of the study. Eligibility deviations are defined in the protocol.

The final IPD list is used to produce the summary of IPDs table and list the subjects with IPDs. In addition, a separate listing of all inclusion and exclusion deviations will be

provided. Important protocol deviations thought to potentially impact the safety of subjects or the interpretation of the analyses will be listed and tabulated using incidence and percentages by deviation type.

The number of subjects reporting Protocol Deviation due to COVID-19 will be summarized in a table. A Protocol Deviation listing of subjects impacted due to COVID-19 will also be provided.

9.4 Demographic and Baseline Characteristics

The following descriptive summaries of demographics and baseline characteristics will be summarized.

Demographics:

- Age (years) at enrollment (continuous summary statistics)
- Age categories (number and percent of subjects 18-64, 65-74, 75-84, >=85 years)
- Sex (number and percentages of males and females)
- Race (number and percentages of subjects in each category or combinations)
- Ethnicity (number and percentages of subjects in each category)

Baseline Characteristics:

- Height and Weight (continuous summary statistics)
- ECOG performance status (frequency and percentages)

9.5 Efficacy Analyses

9.5.1 Analyses of Primary Efficacy Endpoint(s)/Estimand(s)

Not applicable to this study.

9.5.2 Analyses of Secondary Efficacy Endpoint(s)

[figure not shown]
For the secondary efficacy endpoints mentioned below, we will consider the endpoints to be derived and presented separately for the Central review and the Investigator's review except for the overall survival, clinical progression-free survival, time to clinical progression and time to subsequent therapy.

Table 9-1. Secondary Efficacy Endpoint Summary Table

Endpoint	Statistical Analysis	Analysis Set
Objective response per modified Response Evaluation Criteria in	The proportion of subjects with an objective response per modified RECIST 1.1 along with the corresponding	RECIST 1.1 Evaluable Analysis Set

Endpoint	Statistical Analysis	Analysis Set
Solid Tumors (RECIST) 1.1	
exact 95% CI will be calculated using the Clopper-Pearson method (Clopper and Pearson, 1934)
 
Waterfall plots for the maximum percent decrease from baseline in sums of longest diameters will also be provided.
	Applicable for all subjects with measurable baseline disease and at least one post-baseline evaluable tumor response assessment
Overall Survival (OS)	OS will be estimated and the median and other percentiles, as appropriate, will be presented using the Kaplan-Meier curve and 95% CI using Greenwood's formula to estimate the standard error of the landmark estimates, see (Kalbfleisch and Prentice, 1980).	Safety Analysis Set
Radiographic Progression Free Survival (PFS) Clinical Progression Free Survival (clinical PFS)	The median and other percentiles as appropriate, will be presented using the Kaplan-Meier curve and 95% CI using the Brookmeyer and Crowley (Brookmeyer and Crowley, 1982) method.	Safety Analysis Set
Time to Response (TTR)	The median and other percentiles as appropriate, will be presented using the Kaplan-Meier curve and 95% CI using the Brookmeyer and Crowley (Brookmeyer and Crowley, 1982) method.	RECIST 1.1 Evaluable Analysis Set
Time to Progression (TTP) Radiographic Time to Progression (TTP) Clinical	The median and other percentiles as appropriate, will be presented using the Kaplan-Meier curve and 95% CI using the Brookmeyer and Crowley (Brookmeyer and Crowley, 1982) method.	Safety Analysis Set
Duration of Response (DOR)	The median and other percentiles as appropriate, will be presented using the Kaplan-Meier curve and 95% CI using the Brookmeyer and	RECIST 1.1 Evaluable Analysis Set

Endpoint	Statistical Analysis	Analysis Set
	Crowley (Brookmeyer and Crowley, 1982) method.	
Time to subsequent therapy	The median and other percentiles as appropriate, will be presented using the Kaplan-Meier curve and 95% CI using the Brookmeyer and Crowley (Brookmeyer and Crowley, 1982) method.	Safety Analysis Set

9.6 Safety Analyses

9.6.1 Analyses of Primary Safety Endpoint(s)

Table 9-3. Primary Safety Endpoint Summary Table

Endpoint	Statistical Analysis	Analysis Set
Dose Limiting Toxicities (DLTs)	Subject incidence of DLT will be tabulated by planned dose level. A table of DLT will be provided. The probability of subject having a DLT by	DLT Analysis Set

	dose level will be estimated using a modified Toxicity Probability Interval (mTPI) model.	
--	---	--

9.6.2 Adverse Events

The Medical Dictionary for Regulatory Activities (MedDRA) version 25.0 or later will be used to code all events categorized as adverse events to a system organ class and a preferred term and grade. The severity of each adverse event will be graded using CTCAE version 5.0 with the exception of CRS, TLS, and ICANS.

CRS must be graded using the criteria referenced by [Lee et al, 2014](#), TLS must be graded using the criteria referenced by [Coiffier et al, 2008](#), and ICANS must be graded using the criteria referenced by [Lee et al, 2019](#).

The subject incidence of all treatment-emergent adverse events, treatment-related adverse events, serious adverse events, adverse events leading or discontinuation of investigational product or other protocol required therapies, and fatal adverse events will be summarized and tabulated by system organ class and preferred term in alphabetical order.

Subject incidence of all CRS, TLS, and ICANS events will be summarized.

Subject incidence of events of interest (standardized MedDRA queries and/or Amgen Medical Queries) will also be summarized according to their categories, preferred term, and worst severity grade.

Treatment emergent adverse events occurring on or after the COVID-19 infection will be summarized.

A subgroup analysis of safety with CRS outcome and PK will be performed for subjects who were administered siltuximab.

9.6.3 Laboratory Test Results

Clinical chemistry, hematology, and urinalysis data will be reviewed for each subject. Depending on the size and scope of changes in laboratory data the analyses of safety laboratory endpoints will include summary statistics over time and/or changes from baseline over time may be provided.

Shifts in grades of safety laboratory values from baseline for selected laboratory values may also be provided.

9.6.4 Vital Signs and ECOG

Vital signs data will be reviewed for each subject. The analyses of vital signs will include summary statistics over time and/or changes from baseline over time may be provided.

Shifts in scores for ECOG performance status scores between the baseline and each assessed time point will be tabulated and ECOG performance status scores will be summarized at each assessed time points.

9.6.5 Physical Measurements

Physical measurements will be reviewed and listed for each subject.

9.6.6 Electrocardiogram

Summaries over time and/or changes from baseline over time will be provided for all ECG parameters. Subjects' maximum change from baseline in QTcF will be categorized and the number and percentage of subjects in each cohort will be summarized.

Subjects' maximum post baseline values will also be categorized and the number and percentage of subjects in each cohort will be summarized. All on-study ECG data will be listed and select parameters of interest plotted.

9.6.8 Exposure to Investigational Product

Details of AMG 160 administration will be listed for every subject. A listing of unique manufacturing lot numbers and a listing of the subjects administered each manufacturing lot number will be provided.

Descriptive statistics of the total dose (mg), duration of usage, number of cycles, cumulative dose, number and percentage of subjects with dose modifications, reasons for modifications will be produced to describe the exposure to investigational product by treatment group.

9.6.9 Exposure to Non Investigational Product

Subject-level data may be provided instead of the summary if the subject incidence is low or single dose is given. The number of days on non-investigational product, the daily dose, and the proportion of subjects receiving each dose level will be summarized using descriptive statistics.

Compliance with non-investigational product will summarized for each subject using descriptive statistics.

9.6.10 Exposure to Other Protocol-required Therapy

Descriptive statistics of total dose (mg/kg), total dose (mg), average daily dose, cumulative dose, and number of cycles will be produced to describe the exposure to each of the other protocol-required therapy.

9.6.11 Exposure to Concomitant Medication

Number and proportion of subjects receiving therapies of interest will be summarized by preferred term or category for each treatment group as coded by the World Health Organization Drug dictionary.

[figure not shown]
9.7 Other Analyses

The other analyses included in the study are described as below. These exploratory analyses may not be part of the clinical study report.

9.7.1 Analyses of Pharmacokinetic or Pharmacogenetic Endpoints

Serum concentrations of AMG 160 will be determined using a validated assay. PK parameters will include but are not limited to maximum observed concentration (C_{max}), minimum observed concentration (C_{min}) and area under the concentration-time curve over the dosing interval [AUC] and if feasible half-life ($t_{1/2}$). Pharmacokinetic parameters will be estimated using standard non-compartmental approaches based on the PK analysis set and summarized by dose level using descriptive statistics but not limited to means, standard deviations, medians, minimums, and maximums.

Above analysis will be conducted by Amgen Clinical Pharmacology Modeling and Simulation (CPMS).

10. Changes From Protocol-specified Analyses

RECIST 1.1 Evaluable Analysis Set is added for secondary efficacy endpoint evaluation.

Nomenclature referring to rPFS has been removed as rPFS is a specific endpoint for prostate cancer. For this study, the terminology radiographic PFS will be used to assess the RECIST 1.1 endpoints referring to radiographic progression and radiographic progression-free survival.

11. Literature Citations / References

Appendix B. Code Fragments

95% Confidence Interval by Clopper Pearson Method:

```
proc freq data=<data> ;  
tables <variable>*<variable> / binomial (exact);  
run;
```

Kaplan Meier Method and 95% Confidence Interval by Brookmeyer and Crowley

Method:

```
proc lifetest data=<data> method = km conftype = linear alpha = 0.05;  
time T * status (0) ;  
run ;
```

Where T is time to event, status is censoring variable and 0 is flagged for censored observation.

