3.2 Sample Size

Up to 50 subjects will be enrolled in the study (approximately 10 subjects in a dose exploration phase and up to 40 subjects in a dose expansion phase). **Additional subjects (up to 20) may be enrolled in 1 or more monotherapy dose levels that**

have been shown to be safe and tolerable (defined as backfill enrollment). This backfill enrollment may be done to better estimate the RP2D and better characterize the safety, efficacy, PK, and [REDACTED] of AMG 160 monotherapy and may be concurrent with dose escalation to identify the MTD.

An initial 2 to 4 subjects will be enrolled and treated with Dose Level 1 (1 dose level below RP2D of AMG 160 Study 20180101). Rules for dose-escalation/de-escalation are derived using an mTPI model with a target toxicity probability of 0.28. If the dose is not tolerated (based on target DLT rate > 28%), the dose level will be reduced 1 level below the starting dose. Alternative dosing schedules, including further dose escalation as per the ongoing mCRPC trial (Study 20180101), may be explored based on emerging safety and PK data. The sample size in the dose exploration phase is based on practical consideration and is consistent with conventional oncology studies with the objective to estimate the MTD.

[figure not shown]
With 2 subjects in a cohort, there is a 19% to 55% probability of observing at least 1 DLT if the true DLT rate is 10% to 33% and with 4 subjects in a cohort, there is a 34% to 80% probability. With 6 subjects in a cohort, there is a 47% to 91% probability of observing at least 1 DLT if the true DLT rate is 10% to 33% and with 10 subjects in a cohort, there is a 65% to 98% probability.

In the dose expansion phase, a subject number of 40 will provide a 87% probability of observing at least 1 adverse event with 5% incidence rate. An exact 95% binomial CI will be provided for overall response rate. With the 40 subjects and 20% overall response rate, the expected 95% CI would be 9% to 36%.

4. Covariates and Subgroups

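### The linear scale set for Kaplan-Meier confidence intervals under-covers in groups of about 10 or fewer; log-log limits should be specified for medians and for the OS landmark.

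*SAP*

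**What the plan says.** SAP Appendix B gives one survival code fragment. Its heading is "Kaplan Meier Method and 95% Confidence Interval by Brookmeyer and Crowley" and its options are "method = km conftype = linear alpha = 0.05".

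SAP 9.1 assigns Brookmeyer-Crowley to medians and percentiles. For landmark estimates it has the Greenwood formula "used to estimate the standard error used in CI calculation", and adds: "Greenwood formula will be used for landmark analysis". It limits the scope: "We will be only doing the landmark analysis for OS". The OS row of SAP Table 9-1 likewise has "95% CI using Greenwood's formula to estimate the standard error of the landmark estimates".

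Neither place names a scale for the landmark interval, gives a reason for the linear scale, or says what happens to a limit below 0 or above 1.

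On size, SAP 3.2 plans "approximately 10 subjects in a dose exploration phase and up to 40 subjects in a dose expansion phase", with up to 20 backfill subjects on top.

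**The concern.** A linear interval is symmetric about the survival estimate. In a small group the estimate is discrete and skewed, so a symmetric interval is badly placed and its true coverage can fall below 95%. On the survival scale it can also pass 0 or 1.

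Neither named method forces this choice. Greenwood's formula supplies a variance and leaves the scale open. A Brookmeyer-Crowley median interval is read from where the pointwise limits cross 0.5, and those limits can be linear or log-log. The plan is stricter for response rate, where it uses exact Clopper-Pearson limits. For 1-year OS with no censoring, its code would give the ordinary Wald limits for a proportion.

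With no hypothesis test, estimates and intervals are the efficacy result. An interval labelled 95% that covers 84-90% overstates what is known.

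**Working it through.** **The plan's own figures.** No coverage or precision is stated for any survival interval. The nearest figures, in SAP 3.2 for 40 subjects, reproduce: 1 - 0.95^40 = 87.1% (stated 87%), and Clopper-Pearson for 8/40 gives 9.05% to 35.6% (stated 9% to 36%).

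**Inputs.** From the SAP: two-sided alpha 0.05 and linear scale (Appendix B); about 10 in Part 1, up to 40 in expansion, up to 20 backfill (3.2); DOR in responders only (5.1.2). Assumed, because the documents give no expected OS or PFS: 12-month survival of 0.20 to 0.70, and the censoring described below.

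**Formulas.** With estimate S and standard error se (without censoring, se = sqrt(S(1-S)/n)):
- linear: S ± 1.96·se
- log-log: S^exp(±1.96·se/(S·ln S))
- median: from the first event time whose lower limit is ≤ 0.5 to the first whose upper limit is < 0.5

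An estimate of 0 or 1 has no usable interval and is counted as a miss.

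**Landmark, n=10, no censoring (exact binomial).** Take true S = 0.30. Linear limits contain 0.30 when 2 to 6 of 10 survive: 0.2335 + 0.2668 + 0.2001 + 0.1029 + 0.0368 = 0.840. With 1 survivor the linear limits are -0.086 to 0.286, a miss. The log-log limits are 0.006 to 0.358, a hit, which adds 0.121 to give 0.961.

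| True S | Linear | Log-log | A linear limit outside 0-1 |
|---|---|---|---|
| 0.20 | 88.6% | 88.6% | 57.1% |
| 0.30 | 84.0% | 96.1% | 35.6% |
| 0.35 | 88.8% | 98.2% | 25.3% |
| 0.40 | 89.9% | 94.1% | 17.3% |
| 0.50 | 89.1% | 94.4% | 10.7% |
| 0.70 | 84.0% | 92.4% | 35.6% |

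At S = 0.20 the loss is mostly samples with no survivors (0.8^10 = 10.7%), which no change of scale can repair.

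**Median, no censoring (exact).** At n=6 the linear interval runs from the 2nd to the 5th event time and covers (15+20+15)/64 = 78.1%. Log-log runs from the 1st to the 6th and covers 62/64 = 96.9%.

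| n | Linear | Log-log |
|---|---|---|
| 6 | 78.1% | 96.9% |
| 8 | 93.0% | 96.1% |
| 10 | 89.1% | 94.4% |
| 20 | 95.9% | 97.3% |
| 30 | 95.7% | 95.7% |
| 40 | 91.9% | 94.0% |
| 50 | 93.5% | 95.1% |

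**With censoring.** Simulation, 20,000 runs per setting: exponential survival, S(12 months) of 0.20, 0.35 or 0.50, administrative censoring at 12-24 months, 0 or 15% yearly dropout.
- n=10 median: linear 88-89%, log-log 94-96%.
- n=10 landmark: linear 85-89%; log-log 95-98% at S of 0.35-0.50, but 85-88% at 0.20.
- n=20-50: usually 0-3 points apart. The widest gap is 89.6% against 96.3% (landmark, n=20, S=0.20, 15% dropout). Log-log is occasionally lower, for example 92.9% against 94.6% at n=30, S=0.20, no dropout.

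**When a landmark limit leaves 0-1.** Without censoring this needs S < 1.96²/(n + 1.96²) or the mirror value: below 27.8% or above 72.2% at n=10, 16.1% or 83.9% at n=20, and 8.8% or 91.2% at n=40.

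**Width at n=10.** For estimates of 0.3, 0.5 and 0.7, linear landmark intervals are 0.568, 0.620 and 0.568 wide; log-log are 0.507, 0.570 and 0.563. The landmark fault is placement, not width.

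**Where small groups arise.** DOR in 40 subjects: 40 × 0.20 = 8 responders at the SAP 3.2 rate, or 40 × 0.15 = 6 at the futility reference rate. A stop after no response in the first 10 leaves about 10 subjects plus any backfill. Part 1 has its own primary analysis at 6 months (SAP 7.2).

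**The case against.** The strongest reply is that the main survival analyses are not small. SAP Table 9-1 runs OS, PFS, time to progression and time to subsequent therapy on the whole Safety Analysis Set, and Protocol 9.4.2.2 pools subjects treated at the MTD or RP2D. If expansion proceeds, that could be 40-50 subjects, or 70 with full backfill, where the scale matters little. This stands, and it confines the point to small groups.

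Of those groups, the Part 1 analysis is the least certain. SAP 7.2 does not list its endpoints and ties the time-to-event primary analysis to the expansion phase. A stop after Part 1 and DOR with few responders remain realistic. The SAP 7.1 requirement of more than 10 events protects only the interim.

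Several stronger readings are tempting but unsupported:
- **That the code fixes linear limits for the landmark.** The fragment is headed for Brookmeyer-Crowley. For the landmark, linear is an inference from its being the only Kaplan-Meier code.
- **That any survival endpoint can give limits outside 0 to 1.** Median limits are in time units, and SAP 9.1 restricts landmarks to OS.
- **That the squamous cohort will be affected.** SAP 3.1 sets its size at up to 10, but no Kaplan-Meier analysis of it is planned.
- **That linear intervals are simply too narrow.** This holds for medians; at n=10 the linear landmark intervals are the wider ones.
- **That a decision could go wrong.** No hypothesis is tested, and futility rests on response rate.

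**Conclusion.** The point holds for groups of about 10 or fewer. There, linear intervals cover about 84-90% at n=10 and 78% for a median at n=6, against 92-98% with log-log in most settings. The pattern is uneven because coverage is discrete: a median at n=8 without censoring still reaches 93%. At n=20-50 the choice is usually worth 0-3 points.

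Out-of-range limits concern only the OS landmark and pointwise survival limits, and mainly at small n. The exact results assume no censoring; the simulated ones assume exponential survival and the stated censoring. The consequence is overstated precision in secondary, descriptive results. It is worth correcting because the change is nearly free and contradicts nothing else in the plan.

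**What to change.** In SAP Appendix B, replace `conftype = linear` with `conftype = loglog`. In SAP 9.1, state that the Brookmeyer-Crowley intervals for medians and percentiles and the Greenwood-based interval for the OS landmark all use the log-log scale. This also closes the gap on the landmark scale.

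The cost is one code option and one sentence. Median intervals become wider in small groups. Landmark intervals become asymmetric, often without being wider, and stay within 0 to 1. Coverage at n=10 with survival near 0.20 stays at about 85-89% on either scale, so intervals from such a group still need cautious reading.
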